## **AIM 1: To assess the subjective and clinical effects of nicotine reduction on ENDS users.**

Objective and hypothesis. This aim will help understand users' response to NR and how it will influence their product satisfaction, nicotine dependence, intention to quit or use in the future, lung functions, and clinical symptoms. We hypothesize that NR will be associated with less satisfaction, withdrawal suppression, and intention to use in the future and that such an effect will be more pronounced in total compared to partial NR and in high compared to low-frequency users.

Outcomes. We will utilize our clinical lab model to study the effect of NR on the following outcomes assessed according to the plan described in Table 2. All assessments will be based on instruments that are standard in clinical lab studies of addictive behaviors modified for the ENDS we plan to use (Vargas-Rivera et al., 2020). Participants will use a tablet to respond to these measures using RedCap.

**Outcomes.** We will utilize our clinical lab model to study the effect of NR on the following outcomes assessed according to the plan described in Table 2. All assessments will be based on instruments that are standard in clinical lab studies of addictive behaviors modified for the ENDS we plan to use (Vargas-Rivera et al., 2020). Participants will use a tablet to respond to these measures using RedCap. Briefly, we will assess;

1. Demographic and baseline characteristics; including age, race, sex, and reasons for ENDS use. Other characteristics will include the frequency of ENDS use, and the history of other tobacco/nicotine products use (Amato, Boyle & Levy, 2016; Zavala-Arciniega et al., 2019; Vargas-Rivera et al., 2020).
2. Dependence measures including; 1) *Use satisfaction* (Modified Cigarette Evaluation Questionnaire (mCEQ) (Arger et al., 2017); 2) *Dependence* (Questionnaire of Smoking Urges-brief and the Minnesota Nicotine Withdrawal Scale, Penn State Electronic Cigarette Dependence Index (Ben Taleb et al., 2018; Foulds et al., 2015; St Helen et al., 2017); 3) *Puff sensory effects* (Duke Sensory Scale, (Malson & Pickworth, 2002)).
3. Use related measures including 1) *Harm perception* (Smith, Curbow & Stillman, 2007); 2) *Intention to quit or use in the future* (Wackowski et al., 2016); 3) *Reasons for ENDS use* (Kinouani, Pereira & Tzourio, 2017), and 4) Visual Analogue Scale (VAS) to measure ENDS use experience such as pleasantness, enjoyment, and pleasure from use (as in Vargas-Rivera et al., 2020).
4. Lung function tests (LFTs): LFTs (i.e., lung volume testing, airway resistance, specific airway conductance) will be measured before and immediately after ENDS use (Carlos et al., 2019). According to 2019 American Thoracic Society and European Respiratory Society recommendation (Graham, Jacobs & Amato, 2019) simple spirometry (e.g. FVC, % predicted value (pred), FEV1 % pred FEV1/FVC, % pred); forced expiratory flow (FEF) and Peak expiratory flow rate or PEFR) will be performed. Diffusing capacity for carbon monoxide (DLCO) will be determined using a rapidly resolving gas analyzer (RGA) (Neder et al., 2019) and the single-breath technique (Graham et al., 2017).
5. Clinical symptoms, such as (dry mouth, eye irritation, palpitations, and nausea) will be assessed pre-post ENDS use using standard clinical assessments (McConnell et al, 2017; Morice et al., 2007). Symptoms like cough, sore throat will be assessed after-session since our participants will be free of these symptoms pre-session to exclude potential COVID-19 cases (pls. see Inclusion and Exclusion criteria).
6. Cardiovascular measures: To monitor participants' vital signs, physiological measures will be monitored during each session such as heart rate, blood pressure, and pulse oximetry using the Noninvasive Patient Monitor 507E, Criticare Systems, Waukesha, WI.

7. Three-month follow-up call: Assesses Harm perception (Smith, Curbow & Stillman, 2007), *nicotine preference*, and *changes in ENDS and tobacco use* (Amato, Boyle & Levy, 2016; Zavala-Arciniega et al., 2019; Vargas-Rivera et al., 2020).

Table 2: Measures * Only during baseline	Measurement time			
	Pre	During	Post	3 month
Demographics*	X			
Tobacco use history	X			X
ENDS Use satisfaction (mCEQ subscale)			X	
Penn State Electronic Cigarette Dependence Index (10 items)	X			
Questionnaire of Smoking Urges (7-point Likert scale)	X		X	
Minnesota Nicotine Withdrawal Scale (score range from 0-100)	X		X	
ENDS Visual analog scale (0 not at all to 100 extremely)			X	
Duke Sensory Scale (7-point Likert scale)			X	
Peer and family influence	X			
Harm perception	X		X	X
Intention to quit or use in the future	X		X	X
Nicotine preference, changes in ENDS use				X
Reasons for ENDS use	X			
Puff topography (puff volume/ml, duration/sec; inter-puff interval/sec)		X		
Cardiovascular measures (BP; HR; oximetry)		X		
Plasma nicotine (ng/ml)	X		X	
Nicotine (playback)			X	
Aldehydes (playback)			X	

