Individuals with a self-reported history of chronic disease, psychiatric conditions, history of cardiovascular disease, low or high blood pressure (BP) (systolic BP>150 mm Hg, or diastolic BP>100 mm Hg), seizures, or regular use of prescription medications (other than vitamins or birth control) will be excluded (St Helen et al., 2017). This will be assessed by history and physical examination conducted by the research nurse during a screening visit. The research nurse will have access to an on-call Medical Monitor (physician) in case of concern or for consultation at any point during the study (as is the current practice in our lab). The physical examination will include measuring BP, heart rate (HR), temperature, pulse oximetry, and weight/height. Importantly, considering the current COVID-19 pandemic we will follow CDC and FDA guidelines for clinical research and COVID-19 to minimize any potential risk of infection transmission as detailed in our Human Subject Protection part (CDC, 2020b; FDA, 2020c).

Briefly, we will apply a protocol consisting of 5 main areas;

- 1- Screening of Participants for COVID-19;
- 2- Social and Physical Distancing;
- 3- Use of Personal Protective Equipment (PPE);
- 4- Cleaning and disinfecting;
- 5- Personal Hygiene and Hand Washing.

Participants with symptoms/history suggestive of COVID-19 (e.g.  $\geq 100.4^{\circ}\text{F}$ , cough, contact) or with a history of cannabis use (risk for e-cigarette or vaping product use-associated lung injury-EVALI) will be excluded from participation (details in Human Subjects Protection). As knowledge about COVID-19 is rapidly evolving we will apply best practices at the time of study to protect human

subjects and our staff (e.g. require vaccination record if such becomes feasible). FIU has started providing vaccination to all research staff with direct contact with human subjects, and free-of-charge COVID-19 testing facilities have become available within and in the vicinity of FIU (e.g. FIU-Curative., 2020). Women will be excluded if they are breast-feeding or test positive for pregnancy (by urine pregnancy testing) at screening (St Helen et al., 2017). Finally, we will also exclude individuals if they intend to quit e-cigarette within the next 3 month and if they use THC in e-cigarette.

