Screening, and informed consent: Individuals who are identified as potentially eligible based on the phone screening will be asked to attend an onsite-screening, which will involve assessment of inclusion/exclusion criteria, physical examination, COVID-19 screening, and urine pregnancy testing for women. Prior to screening, potential participants will undergo a review of the study and consent procedures to ensure that they understand the study, its risks/benefits, and their rights as research participants. Consented (written) individuals will then undergo a physical examination conducted by the research nurse, who will have access to an on-call Medical Monitor (physician) in case of concern or for consultation at any point of the study as it is the standard practice in our lab. Successfully consented participants will be scheduled for their 1st session and asked to abstain from all tobacco/nicotine use 12 hours prior to it.

Sample size. All power calculations were performed with PASS19 (PASS, 2019). We built our calculation of the sample size for this study based on our preliminary study of the effect of NR on subjective (e.g. craving, urges) and puff topography measures (pls. see Preliminary Studies), where medium effect size (Cohen's  $f=0.2$ ) depending on nicotine condition was detected. Expecting a maximum 20% loss due to noncompliance with abstinence or study protocol (Vargas-Rivera et al., 2020), this study will include a dropout inflated sample of 150 ENDS users. Using repeated measures ANOVA F-test with 2 within and 1 between factors, a total dropout adjusted sample size of 120 (2X60) participants will have at least 80% power to detect small to medium-size effect (Cohen's  $f=0.1-0.2$ ) or larger for 2 within-subject (NR condition and time) and 1 between subject (use frequency) factors, as well as their interactions at 0.05 level of significance, assuming sphericity and a moderate correlation (0.5) among repeated measures (Cohen, 1988).

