Experimental protocol. Participants from each frequency group will be randomly assigned to one of the nicotine concentration conditions and attend the lab for two, ~2-h sessions, separated by a 48-h washout period, and differ by nicotine concentration (3%,5%) or (0%, 5%). Session order will be counterbalanced to mitigate order and carry-over effects. At the beginning of the 1st session, participants will provide consent, complete demographic and personal information including age, sex, socioeconomic status, race/ethnicity, and detailed tobacco/nicotine use history. Participants will get familiarized with the study procedures, measures, and they will be given time to adapt to the lab. After adaptation, continuous measurement of physiological responses begins, and 10 ml of venous blood is sampled, lung function tests will be conducted, and participants are asked to respond to subjective measures (pls. see below Outcome Measures). Participants will inhale on their session ENDS ad libitum for up to 60 minutes (as in Vargas-Rivera et al., 2020). At the end of the ENDS use period 10 ml of blood will be sampled, lung function tests repeated, and subjective measures assessed. The session will terminate 30 minutes after the last puff, and the 2nd session is scheduled. A follow-up phone call at 3-month post-study will be made to evaluate nicotine preferences and changes in ENDS and tobacco use.

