Demographic data will be examined and compared to determine if there are significant between-group differences on measures that may be related to study outcome (some differences are expected due to design such as past 30-day ENDS use) though these are expected to be minimized due to randomization. Unexpected between-group differences will be considered as potential adjustment covariates in the primary analysis (Evans et al., 2006). We will generate descriptive statistics which include means, standard deviations, frequencies, and proportions depending on the scale of the outcome by NR factor, time and group assignment. Univariate comparisons of the outcomes by the mentioned conditions will consist of repeated measures ANOVA and paired t-test (for 2X2 within factors) and two-sample t-test for between factor, or their non-parametric equivalents (Wilcoxon signed-rank test and Friedman test for within factors and Wilcoxon Mann-Whitney U test for between factor) if the parametric assumptions are not met. ANOVA will be followed by multiple comparisons with Bonferroni adjustments for multiplicity. Analysis of categorical outcomes will involve a chi-square test of independence for between factors or McNemar's test for paired proportions. The primary analysis of each outcome will involve analysis of variance with two within-subject factors (nicotine concentration: (5%, 3%) or (0% 5%)) and time (pre-post-use). This approach will be extended into a mixed-effects linear regression model to adjust or study the effects of personal attributes such as sex, education, race, and SES. Furthermore, we will consider clinical/physiologic factors such as lung function and respiratory symptoms in a similar modeling approach described above, as a function of experimental factors and demographic covariates, in order to quantify the harm or disease risk. In a case of a non-linear relationship between these factors, we will apply outcome transformations or use non-linear splines to accurately describe these outcomes as a function of

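### Cough and sore throat have no recorded pre-use value at either session, so post-use reports cannot be shown to be new and cannot enter the stated pre-post analysis

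*Combined protocol and SAP*

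**What the plan says.** In AIM 1, Outcomes, item 5, dry mouth, nausea, palpitations and eye irritation "will be assessed pre-post ENDS use using standard clinical assessments". Cough and sore throat are handled differently: "Symptoms like cough, sore throat will be assessed after-session since our participants will be free of these symptoms pre-session to exclude potential COVID-19 cases". The stated reason is the COVID-19 exclusion.

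The places that bear on that reason are these:

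- Participants and recruitment, inclusion and exclusion criteria: "Participants with symptoms/history suggestive of COVID-19" are excluded. The bracketed examples include cough but not sore throat. "Screening of Participants for COVID-19" is one of five areas of the infection-control protocol, and the detail is deferred to the human subjects section.
- Same section, screening and informed consent: the on-site screening is the visit "which will involve assessment of inclusion/exclusion criteria, physical examination, COVID-19 screening, and urine pregnancy testing for women".
- Same section, abstinence procedure: the hour before each session covers observation and a CO test.
- Same section, experimental protocol: the pre-use steps are physiological monitoring, blood sampling, lung function tests and subjective measures. The two sessions are 48 hours apart.
- Statistical analysis: "The primary analysis of each outcome will involve analysis of variance with two within-subject factors", namely nicotine concentration and time (pre-post). Respiratory symptoms are also to be modelled to quantify harm.

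**The concern.** A pre-post outcome needs a pre value. For these two symptoms the plan replaces it with an assumption of absence, and the text does not show that the assumption is checked on the day. A regular ENDS user could pass screening and later arrive at session 1 or session 2 with an irritated throat. Nothing in the listed steps would record it.

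Two things are at stake. First, a post-use report cannot be classed as new or as already present, so the absolute rate of acute respiratory symptoms may be overstated. Second, the stated primary analysis cannot be run for these symptoms as written. Session 2 adds a smaller point: a symptom that began after session 1 has no place to be recorded before the second exposure, although the plan intends to test for carry-over. A baseline that was not asked for cannot be recovered afterwards.

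**Working it through.** The plan gives no figure for symptom rates, so there is none to reproduce. The check is a reading of the timing, followed by an illustration of size.

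**Timing.** Item 5 rests on participants being free of symptoms at the start of each session. Set against that:

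1. The only dated COVID-19 screen is the on-site screening visit, which comes before session 1 is scheduled.
2. Neither the pre-session hour nor the pre-use steps name a symptom check at session 1 or session 2.
3. Cough is a named exclusion example; sore throat is not.
4. Protection of human subjects, as available here, contains no COVID-19 detail, so it does not settle whether the screen is repeated.

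**Analysis.** With no pre value, the time factor and the nicotine-by-time interaction have nothing to estimate from. If the analyst enters none for every participant, the pre cell has no variation and the pre-post change equals the post value by construction. The interaction then reduces to the post-use contrast between conditions. Multiple imputation does not help, because the pre value is observed for nobody.

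**Size.** Let q be the share of sessions that start with the symptom and p the true rate of new onset among the rest. Assume that a symptom present at the start is reported again after use, and that q is the same in both nicotine conditions. The documents give neither q nor p, so all values below are assumptions.

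- Observed post-use rate = q + (1 − q)p. With p = 10%: at q = 5%, 0.05 + 0.95 × 0.10 = 14.5%; at q = 20%, 0.20 + 0.80 × 0.10 = 28%.
- Observed difference between conditions = (1 − q)(pA − pB). With true rates of 30% and 15%: at q = 5%, 0.95 × 15 = 14.25 points; at q = 20%, 0.80 × 15 = 12 points.

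| Assumed q | Observed rate, true 10% | Difference, true 20% v 20% | Difference, true 30% v 15% |
|---|---|---|---|
| 0% | 10.0% | 0 | 15.0 points |
| 2% | 11.8% | 0 | 14.7 points |
| 5% | 14.5% | 0 | 14.25 points |
| 10% | 19.0% | 0 | 13.5 points |
| 20% | 28.0% | 0 | 12.0 points |

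AIM 3 counts 240 topography sessions (120 participants × 2). On that count, q = 5% is 240 × 0.05 = 12 sessions and q = 20% is 240 × 0.20 = 48 sessions that start with an unrecorded symptom.

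**The case against.** The strongest reply is that the plan does screen for these symptoms. It excludes people with signs of COVID-19, names cough among them, and makes participant screening a standing part of its protocol. The dated screen is not said to be the only one. A reader might infer that no pre-session check exists. The documents do not support that: they support only that a check at each session is not stated. Table 2 adds little here, because it omits every clinical symptom, including the four that the text places before and after use. This part of the reply stands. It does not supply the missing value, however, because even a repeated screen would leave item 5 without a recorded pre-use answer.

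A reader might also infer that pre-existing symptoms are being counted as product effects. That would require symptoms that arise after screening or go undetected, and the documents do not show that this happens. The supportable statement is that the two cannot be told apart.

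Third, the main question is a within-person comparison of nicotine concentrations with counterbalanced order. On equal q, a null contrast stays null and a true contrast shrinks by the factor 1 − q. This stands, and it limits the damage.

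Fourth, other outcomes are post-only by design, such as use satisfaction and the visual analogue scale, and McNemar's test could compare post-use symptoms between conditions. That is true. But those scales rate the product just used, whereas cough and sore throat can be present before use. Aim 1 promises pre-post symptom assessment, although its listed examples do not include these two.

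Finally, since post-use steps are listed as "lung function tests repeated, and subjective measures assessed", one might infer that forced breathing provokes the cough that is then recorded. The text does not name the symptom form in that list or clearly fix the order, and any such effect would arise under both conditions. Moving the form ahead of the lung tests would also compete with the requirement that those tests follow use immediately. That inference should not be pursued.

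**Conclusion.** The concern holds in limited form. Cough and sore throat have an assumed pre-use value, the plan does not state a symptom check at the start of either session, and the stated nicotine-by-time analysis cannot be applied to them. This conclusion rests on the text alone and needs no assumed prevalence.

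The size does depend on assumptions. With a true onset rate of 10%, the observed rate runs from 10% at q = 0 to 28% at q = 20%. If the exclusion is enforced at each session, q should be near the lower end. The error falls mainly on the absolute post-use rate and the pre-post change. The contrast between nicotine conditions is only attenuated, slightly so for q up to 10%, provided that q does not differ by condition. The documents do not support a claim that the comparison between concentrations is invalid.

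**What to change.** 1. Put cough and sore throat on the same pre-use symptom form as the other four symptoms, at both sessions.
2. At session 2, word the item to cover the time since session 1, with answers that separate a symptom still present from one that has resolved.
3. Use the pre-use answer as the session baseline in the pre-post analysis.
4. Add a clinical-symptom row (Pre, Post) to Table 2.
5. State whether the COVID-19 symptom screen is repeated at each session, so that item 5 and the screening text agree.

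The cost is two extra questionnaire items per session on the tablet already in use, with no added visit or procedure. The downside is that the items will be nearly constant if the exclusion is enforced at each session. In that case they document the assumption on which item 5 now relies. The order of the post-use form and the lung function tests can stay as it is.

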## **AIM 2: To assess the puffing behavior in response to nicotine reduction.**

**Objective and hypothesis.** This aim will help understand users' compensatory puffing behavior in response to NR and its effect on plasma nicotine as the main substance sustaining addiction to ENDS. *We hypothesize that NR-related compensatory puffing will be more pronounced in high vs. low-frequency users.*

### **Outcomes.**

1. Puff topography: Puff topography will be measured with a device that was developed for ENDS (Spindle et al., 2015, 2018; Hiler et al., 2017) and adapted for JUUL (Vargas-Rivera et al., 2020). The software converts signals to airflow (ml/sec) and integrates the flow data, producing measures of puff volume, duration, number, and interpuff interval (IPI).
2. Plasma nicotine: Plasma nicotine is a standard measure in acute effects lab models for tobacco products (e.g., [name] et al., 2019b). Blood samples (~10 ml) will be drawn via a butterfly needle from the participants' forearm vein before ENDS use session onset and within 10 minutes of its end. Plasma samples will be frozen immediately at -80°C, to be analyzed later by our Forensic Chemistry Lab at FIU using Liquid Chromatography Mass Spectrometry (Jacob et al., 2000; [name] et al., 2019b).

## **AIM 3: To assess exposure to toxicants associated with nicotine reduction.**

**Objective and hypothesis:** This aim will help elucidate how compensatory puffing behavior in response to NR affects exposure to pulmonary toxicants. *We hypothesize that partial but not total NR will be associated with compensatory puffing behavior that will, in turn, lead to greater exposure to toxicants.*

**Analytical methods.** The analytical assessments will be conducted at the AUB Aerosol Research Laboratory (ARL). The ARL is equipped with two digital playback smoking machines necessary for Aim 3. These two machines, developed and tested by our team at AUB, are to our knowledge unique to this setting and are not available in any other laboratory. The proposed work in Aim 3 is built on the ARL framework and infrastructure for aerosol generation, sampling, and chemical analysis.

**Aerosol generation and sampling:** The deidentified puff topography data will be shared via Microsoft Sharepoint between FIU and AUB Aerosol Lab, thus, all communication will be encrypted between client and server using SSL 2048 bit keys. Access to the lab and data will be granted only by permission of Drs. [name] (PI), and [name] (local PI at AUB).

Once the puff topography files have been received by the ARL, we will use ALVIN (Aerosol Lab Vaping Instrument) (Talih et al., 2015, 2017) to draw aerosols from the ENDS devices, for each of the 240 topography sessions. For each session, ALVIN will be programmed to reproduce the puff topography data generated in the clinical lab. The generated aerosol will be drawn through a Gelman type A/E 47mm glass fiber filter followed by a 2,4-dinitrophenylhydrazine-coated silica cartridge (type LpDNPH H10) cartridge, for nicotine and aldehydes quantification, respectively (see Talih et al., 2015, 2017; El-Hellani et al., 2018 for more detail). The pods (e.g. JUUL) and batteries will be shipped from the same batch as those used at FIU to minimize biases. A new pod will be used for every session. Each pod will be pre-conditioned before sampling by drawing 15 4-second puffs at 1 LPM using ALVIN. We will use a quality assurance protocol and ENDS electrical performance tester developed at the ARL to ensure that each battery and pod are within tolerance (Talih et al., 2019, 2020b).

**Chemical analysis:** The ARL is equipped with gas chromatographs with a flame ionization detector and a mass spectrometer (GC-FID, GC-MS), as well as and High-performance liquid chromatography-Mass Spectrometry (HPLC-MS) for nicotine and aldehydes analysis. ARL optimized analytical methods have been used in several NIH-funded studies of ENDS nicotine and aldehydes emissions (El-Hellani et al., 2018; Talih et al., 2014).

